### **7.2.5 Sponsor Responsibility for Reporting Adverse Events**

All Adverse Events will be reported to regulatory authorities, IRB/IECs and investigators in accordance with all applicable global laws and regulations.

## **7.3 TRIAL GOVERNANCE AND OVERSIGHT**

### **7.3.1 Efficacy and Safety Evaluation Committee**

The Efficacy and Safety Evaluation Committee (ESEC) will be established for the purpose of evaluating the safety information of this study from the specialist and objective viewpoints to ensure the safety of subjects.

The details of the ESEC are prescribed by separate instructions.

### **7.3.2 Independent Pulmonary Radiographic Adviser**

An independent pulmonary radiographic adviser will review pulmonary radiographic changes and its features using chest CT imaging. The details of the independent pulmonary radiographic adviser are prescribed by separate instructions.

## **8.0 STATISTICAL ANALYSIS PLAN**

### **8.1 Statistical Analysis Plan Summary**

This section contains a brief summary of the statistical analyses for this trial. Full detail is in the Statistical Analysis Plan (SAP) (Section 8.2).

The primary purpose of this study is to investigate the safety, tolerability, and anti-tumor activity of MK-3475 administered intravenously to subjects with advanced melanoma.

#### **8.1.1 Efficacy Analyses**

The full analysis set (FAS) population (defined as all subjects with a baseline scan with measurable disease and who either have a post baseline scan or discontinue the trial due to progressive disease or a drug-related AE) will serve as the primary population for the analyses of efficacy data in this trial. Overall response rate based on RECIST 1.1 will be used as the primary endpoint for efficacy assessment. A 95% confidence interval along with a one-sided p-value for testing the null hypothesis (ORR=10%) based on the binomial distribution will be provided for the response rate. The study is considered to have reached the efficacy objective if the corresponding p-value for testing the respective null hypothesis is less than 2.5%. An outline of the efficacy analysis strategy is presented in [Table 8](#) below.

Table 8 Primary Analysis Strategy for Efficacy Endpoints

Endpoint/Variable (Description, Time Point)	Statistical Method	Analysis Population	Missing Data Approach
Primary:			
Overall RECIST 1.1 response rate based on central radiology review	Exact test of binomial parameter	FAS	Subjects with missing data are considered non-responders
Secondary:			
Overall RECIST 1.1 response rate based on site assessment	Exact methods for binomial parameter	FAS	Subjects with missing data are considered non-responders
Progression-free survival (RECIST 1.1)	Summary statistics using Kaplan-Meier method	FAS	Censored at last assessment
Response duration (RECIST 1.1)	Summary statistics using Kaplan-Meier method	All responders	Non-responders are excluded in analysis
Overall survival	Summary statistics using Kaplan-Meier method	FAS	Censored at last assessment
Overall irRC response rate based on central radiology review	Exact methods for binomial parameter	FAS	Subjects with missing data are considered non-responders
Progression-free survival (irRC)	Summary statistics using Kaplan-Meier method	FAS	Censored at last assessment
Response duration (irRC)	Summary statistics using Kaplan-Meier method	All responders	Non-responders are excluded in analysis

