## **5.8 Subject Withdrawal/Discontinuation Criteria**

Subjects may withdraw consent at any time for any reason or be dropped from the trial at the discretion of the investigator should any untoward effect occur. In addition, a subject may be withdrawn by the investigator or the Sponsor if enrollment into the trial is inappropriate, the trial plan is violated, or for administrative and/or other safety reasons. Specific details regarding discontinuation or withdrawal procedures; including specific details regarding withdrawal from Future Biomedical Research, are provided in Section 7.1.4 – Other Procedures.

A subject must be discontinued from the trial for any of the following reasons:

- The subject or legal representative (such as a parent or legal guardian) withdraws consent.
- The marketing approval of MK-3475 for melanoma, the completion of all safety follow-up or the time when a possibility of entry to second course is lost (e.g. the time of decision by investigator or subject for no enter to second course, the start of a new anti-cancer therapy, the delivery of marketed product of MK-3475 in each site, 6 months from marketing approval), whichever occurs last

A subject must be discontinued from treatment (but may continue to be monitored in the post-treatment follow-up portion of the trial) for any of the following reasons:

- Radiographic disease progression

Note: A subject may be granted an exception to continue on treatment with confirmed radiographic progression if clinically stable or clinically improved, please see Section 7.1.3.4

- Unacceptable adverse experiences as described in Section 5.2.1.2
- Intercurrent illness that prevents further administration of treatment
- Completed 24 months of treatment with MK-3475

Note: 24 months of study medication is calculated from the date of first dose. Subjects who stop MK-3475 after 24 months may be eligible for up to 1 year of additional study treatment if they progress after stopping study treatment provided they meet the requirements detailed in Section 7.1.5.2.1.

- Investigator's decision to withdraw the subject
- The subject has a confirmed positive serum pregnancy test
- Noncompliance with trial treatment or procedure requirements

- The subject is lost to follow-up
- Administrative reasons
- The delivery of marketed product of MK-3475 in each site
- 6 months from marketing approval for melanoma

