### **8.2.3 Analysis Endpoints**

#### **8.2.3.1 Efficacy/Immunogenicity/Pharmacokinetics Endpoints**

Efficacy and safety endpoints that will be evaluated for are listed below, followed by the descriptions of the derivations of selected endpoints.

The primary efficacy endpoint is response rate, defined as the proportion of subjects in the analysis population who have complete response (CR) or partial response (PR) using RECIST 1.1 criteria at any time during the study. Response for the primary analysis will be determined by the central independent radiology review.

Key secondary efficacy endpoints include:

- Response rate based on site assessments using RECIST 1.1

Other secondary efficacy endpoints include: (1) duration of response, defined as time from first RECIST 1.1 response to disease progression in subjects who achieve a PR or better; (2) progression-free survival (PFS), defined as the time from allocation to the first documented disease progression according to RECIST 1.1 or death due to any cause, whichever occurs first; (3) overall survival (OS) ; (4) Response rate based on irRC ; (5) duration of response based on irRC and (6) progression-free survival (PFS) based on irRC.

Immunogenicity/pharmacokinetics endpoints are exploratory endpoints in this study. Immunogenicity endpoint include anti-MK-3475 antibody and pharmacokinetics endpoints include pharmacokinetic parameters of MK-3475.

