### **8.2.4 Analysis Populations**

#### **8.2.4.1 Efficacy Analysis Populations**

The Full Analysis Set (FAS) population will serve as the primary population for the analysis of efficacy data in this study. The FAS population consists of all allocated subjects with subjects excluded for the following reasons:

- Failure to receive at least one dose of study treatment,
- Lack of baseline data for those analyses that require baseline data

Details on the approach to handling missing data are provided in Section 8.2.5 Statistical Methods.

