### 8.2.5.1 Statistical Methods for Efficacy Analyses

For the primary efficacy endpoint centrally reviewed RECIST 1.1 response rate, the point estimate, 95% confidence interval, and p-value for testing the RECIST 1.1 response rate is greater than the historical control will be provided using exact binomial distribution. Subjects in the primary analysis population (FAS) without response data will be counted as non-responder.

Secondary efficacy evaluations of RECIST 1.1 response based on investigator assessment will also be conducted using the same methodology as for the primary efficacy analysis.

For PFS endpoint, Kaplan-Meier (KM) curves and median estimates from the KM curves will be provided as appropriate. Subjects without efficacy evaluation data or without survival data will be censored at Day 1. [Table 9](#) summarizes the key efficacy analyses.

Table 9 Analysis Strategy for Key Efficacy Variables

Endpoint/Variable ‡ (Description, Time Point)	Primary vs. Supportive Approach †	Statistical Method	Analysis Population	Missing Data Approach
Primary Hypothesis #1				
Overall RECIST 1.1 response by central radiology assessment	P	Exact test of binomial parameter	FAS	Subjects with missing data are considered non-responders
Secondary Hypothesis #1				
Overall RECIST 1.1 response rate based on site assessment	P	Exact methods for binomial parameter	FAS	Subjects with missing data are considered non-responders
Progression-free survival (RECIST 1.1)	P	Summary statistics using Kaplan-Meier method	FAS	Censored at last assessment
Response duration (RECIST 1.1)	P	Summary statistics using Kaplan-Meier method	All responders	Non-responders are excluded in analysis
Overall survival	P	Summary statistics using Kaplan-Meier method	FAS	Censored at last assessment
Overall irRC response rate based on central radiology review	P	Exact methods for binomial parameter	FAS	Subjects with missing data are considered non-responders
Progression-free survival (irRC)	P	Summary statistics using Kaplan-Meier method	FAS	Censored at last assessment
Response duration (irRC)	P	Summary statistics using Kaplan-Meier method	All responders	Non-responders are excluded in analysis

† P=Primary approach; S=Secondary approach.

The strategy to address multiplicity issues with regard to multiple efficacy endpoints is described in Section 8.2.6, Multiplicity and Section 8.2.9, Interim Analyses.

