### **8.2.7 Sample Size and Power Calculations**

In this study, approximately total 35 subjects with advanced melanoma will be enrolled, among them at least 28 from cutaneous melanoma and at most 7 from mucosal melanoma. The 28 cutaneous melanoma subjects are the main analysis population. 7 subjects with mucosal melanoma are population for exploratory analysis.

With approximately 28 evaluable subjects with cutaneous melanoma, the study has approximately 90% power to detect a 25% difference in ORR under the null hypothesis of ORR=10% with a type I error rate of 2.5% if the true ORR is 35%. The null hypothesis rate of 10% is based on the historic response rate in large phase III trials for standard single agent chemotherapy in melanoma [21-30]. Success for this hypothesis requires at least 7/28 responses. The actual number of subjects enrolled may be larger than 28 to ensure that at least 28 subjects are evaluable for primary analysis.

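### Sections 8.1.1 and 8.2.4.1 define the full analysis set differently, and the 8.1.1 version drops some unscanned subjects whom 8.2.4.1 and 8.2.5.1 keep as non-responders

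*Combined protocol and SAP*

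**What the plan says.** Both sections name the FAS as the primary population for efficacy.

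- **Section 8.1.1** requires a baseline scan with measurable disease and admits subjects "who either have a post baseline scan or discontinue the trial due to progressive disease or a drug-related AE".
- **Section 8.2.4.1** sets no post-baseline condition: "The FAS population consists of all allocated subjects with subjects excluded for the following reasons". The two reasons listed are never having been dosed and lacking baseline data for an analysis that needs them.
- **Section 8.2.5.1** handles missing response: "Subjects in the primary analysis population (FAS) without response data will be counted as non-responder". Tables 8 and 9 repeat the rule.
- **Section 8.1** calls itself a brief summary and sends the reader to 8.2 for full detail. It does not say which text prevails in a conflict.
- **Section 8.2.7** sizes the trial on 28 *evaluable* cutaneous subjects and adds: "The actual number of subjects enrolled may be larger than 28 to ensure that at least 28 subjects are evaluable for primary analysis". Section 8.1.3 says much the same. Neither defines *evaluable*.

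Tables 8 and 9 also use the FAS for PFS and OS.

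**The concern.** The two definitions cannot both be applied, and the FAS supplies the denominator of the trial's only confirmatory test. The non-responder rule does not settle the matter, because it reaches only subjects already in the FAS, and the 8.1.1 condition removes the subjects in question first.

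The first scheduled on-study scan is at week 12, which leaves time for a dosed subject to leave unscanned. The subjects affected are those who withdraw consent, are lost to follow-up, start new therapy, or die without progression or a drug-related adverse event being recorded as the reason.

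The direction is fixed. A responder must have a post-baseline scan, so the post-baseline condition removes only non-responders. (The separate measurable-disease condition at baseline has no fixed direction.) The trial is open-label, so the choice should not be left until results are known.

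Survival is touched as well. An early unscanned death of this kind is an OS event under 8.2.4.1 and disappears under 8.1.1.

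**Working it through.** **Inputs.** Null ORR 10%, exact one-sided binomial test, success if p < 0.025 (8.1.1, 8.2.6). True ORR 35%, 28 subjects, at least 7 responses (8.1.3, 8.2.7). The plan allows more than 28 cutaneous subjects; I take 28 to 35. The documents give no rate of exclusion, so the rates below are assumptions.

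**The plan's own figures.** With X ~ Bin(28, p):
- P(X ≥ 7 | p = 0.10) = 0.0179, and P(X ≥ 6 | p = 0.10) = 0.0550, so 7 is the smallest valid cut-off.
- P(X ≥ 7 | p = 0.35) = 0.9077, against a stated power of about 90%. Both figures reproduce.

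**Who differs.** Take a dosed subject with measurable disease at baseline and no post-baseline scan.

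| Reason for leaving | 8.1.1 | 8.2.4.1 with 8.2.5.1 |
|---|---|---|
| Progression or drug-related AE | in, non-responder | in, non-responder |
| Consent withdrawn, lost, new therapy, other death | out | in, non-responder |

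A subject who only stops treatment for an unrelated adverse event is normally in both sets. Section 5.8 says such subjects must stop treatment "but may continue to be monitored in the post-treatment follow-up portion of the trial", and 7.1.3.4 and 7.1.5.4.2 call for 12-weekly imaging.

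**When the verdict changes.** The exact cut-off is 6 for n = 18–23, 7 for n = 24–29 and 8 for n = 30–35. A reversal needs one responder fewer than the cut-off and enough exclusions to reach the next lower step.

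- 28 treated, 6 responders: 6/28 p=0.0550; 6/27 p=0.0471; 6/26 p=0.0399; 6/25 p=0.0334; 6/24 p=0.0277; 6/23 p=0.0226. Five exclusions are needed.
- 30 treated, 7 responders: 7/30 p=0.0258; 7/29 p=0.0216. One is enough.
- Exclusions needed for n = 28, 29, …, 35: 5, 6, 1, 2, 3, 4, 5, 6.

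**How often.** Let each treated subject be excluded with probability d, so E ~ Bin(n, d), all non-responders. Responders among the rest follow Bin(n − E, p/(1 − d)), which keeps the ORR over all dosed subjects at p. The chance that the two definitions disagree on success at p = 0.35 is:

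| d (assumed) | n = 28 | n = 30 | range, n = 28–35 |
|---|---|---|---|
| 2% | 0.0% | 3.3% | 0–3.3% |
| 5% | 0.1% | 5.5% | 0.03–5.5% |
| 10% | 1.3% | 6.6% | 0.6–6.6% |
| 15% | 3.2% | 7.6% | 1.7–7.6% |

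**Effect on the estimate.** With 10 responders among 28 and two dropped, 10/28 = 35.7% (Clopper-Pearson 95% CI 18.6–55.9) becomes 10/26 = 38.5% (20.2–59.4).

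**Effect on OS.** One early unscanned death of this kind among 28, with no other early death, gives 27/28 = 96.4% alive at week 12 under 8.2.4.1 and 27/27 = 100% under 8.1.1. This is an illustration; week-12 survival is not an endpoint of the plan.

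**The case against.** The best reply is that 8.2 governs. Section 8.1 is only a summary, and the detailed text is consistent: 8.2.4.1 keeps these subjects and 8.2.5.1 counts them as non-responders. That is the natural reading and it limits the weight of the point. It does not remove the conflict, because 8.1.1 does not abbreviate 8.2.4.1 but states a different set, and *evaluable* can be read as the 8.1.1 set.

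The second reply is that few subjects are involved. Entry requires ECOG 0–1, LDH at or below the upper limit of normal and a life expectancy of at least 3 months, and imaging continues after most treatment stops. This stands. The one-exclusion reversal needs about 30 treated subjects and exactly 7 responders.

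A reader might infer that 8.1.1 inflates the type I error. The documents do not support that. With the 10% null placed on all dosed subjects, the error under 8.1.1 for n = 28–35 is at most 2.2% at d = 2% or 5%, 2.1–2.6% at 10% and 2.9–3.3% at 15%. With the null placed on the 8.1.1 set instead, it is 1.3–1.5% at 15% and stays below 2.5% at all four rates. The 10% comes from cited trials whose denominators are not given, so neither placement can be called the right one from the documents.

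On survival, OS and PFS are descriptive Kaplan-Meier summaries without a test, so no formal conclusion turns on them. For PFS there is also a separate conflict. Section 8.2.3.1 counts progression "according to RECIST 1.1 or death due to any cause, whichever occurs first", while 8.2.5.1 says: "Subjects without efficacy evaluation data or without survival data will be censored at Day 1". Aligning the FAS would not settle that.

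**Conclusion.** The inconsistency is real, stands in current text, and should be corrected. It concerns one narrow group: dosed subjects without a post-baseline scan who leave for a reason other than progression or a drug-related adverse event. A reader might take 8.1.1 to remove every never-scanned subject. It does not, since those who discontinue for progression or a drug-related adverse event stay in.

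The post-baseline condition can only raise the ORR. At 28 treated cutaneous subjects the verdict is safe unless five or more are excluded. Under the assumed rates of 2–15%, the definitions disagree on success in 0–3.2% of trials at n = 28 and in at most 7.6% for n up to 35. The ordinary consequence is an estimate a few points higher, and early deaths of this kind missing from OS. These figures rest on assumed exclusion rates, independent exclusions and a true ORR of 35%.

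The point does not call the sample size, the power or the 7/28 rule into question.

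**What to change.** Replace the definition in parentheses in 8.1.1 with that of 8.2.4.1: all allocated subjects with at least one dose and the baseline data the analysis requires. State there that a subject with no post-baseline scan counts as a non-responder. In 8.1.3 and 8.2.7, define *evaluable* as membership of this FAS among cutaneous subjects. The 8.1.1 set may be kept as a labelled sensitivity analysis, though resolving the conflict does not require it.

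The cost is wording only. No new data are needed and the design figures for 28 subjects do not change. The reported ORR may be slightly lower than under 8.1.1.

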### 8.1.2 Safety Analyses

The All-Patients-as-Treated population will be employed for safety analyses.

### 8.1.3 Power and Sample Size

In this study, approximately total 35 subjects with advanced melanoma will be enrolled, among them at least 28 from cutaneous melanoma and at most 7 from mucosal melanoma. The at least 28 cutaneous melanoma subjects are the main analysis population. At most 7 subjects with mucosal melanoma are population for exploratory analysis.

With approximately 28 evaluable subjects with advanced cutaneous melanoma, the study has approximately 90% power to detect a 25% difference in ORR under the null hypothesis of ORR=10% with a type I error rate of 2.5% if the true ORR is 35%. Success for this hypothesis requires at least 7/28 responses. The actual number of subjects enrolled may be larger than 28 to ensure that at least 28 subjects are evaluable for main analysis.

## **8.2 Statistical Analysis Plan**

### **8.2.1 Responsibility for Analyses/In-House Blinding**

The statistical analysis of the data obtained from this study will be the responsibility of the Clinical Biostatistics department of the SPONSOR.

This trial is being conducted as an open-label study, i.e., subjects, investigators, and SPONSOR personnel will be aware of subject treatment assignments after each subject is enrolled and treatment is assigned.

The Clinical Biostatistics department will generate the allocation schedule(s) for study treatment assignment.

### **8.2.2 Hypotheses/Estimation**

Objectives and hypotheses of the study are stated in Section 3.0.

### **8.2.3 Analysis Endpoints**

#### **8.2.3.1 Efficacy/Immunogenicity/Pharmacokinetics Endpoints**

Efficacy and safety endpoints that will be evaluated for are listed below, followed by the descriptions of the derivations of selected endpoints.

The primary efficacy endpoint is response rate, defined as the proportion of subjects in the analysis population who have complete response (CR) or partial response (PR) using RECIST 1.1 criteria at any time during the study. Response for the primary analysis will be determined by the central independent radiology review.

Key secondary efficacy endpoints include:

- Response rate based on site assessments using RECIST 1.1

Other secondary efficacy endpoints include: (1) duration of response, defined as time from first RECIST 1.1 response to disease progression in subjects who achieve a PR or better; (2) progression-free survival (PFS), defined as the time from allocation to the first documented disease progression according to RECIST 1.1 or death due to any cause, whichever occurs first; (3) overall survival (OS) ; (4) Response rate based on irRC ; (5) duration of response based on irRC and (6) progression-free survival (PFS) based on irRC.

Immunogenicity/pharmacokinetics endpoints are exploratory endpoints in this study. Immunogenicity endpoint include anti-MK-3475 antibody and pharmacokinetics endpoints include pharmacokinetic parameters of MK-3475.

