### 3.2 Secondary Objective(s) & Hypothesis(es)

- 1) **Objective:** To evaluate the duration of response (DOR) and progression-free survival (PFS) per RECIST 1.1 assessed by the central independent radiology review in subjects with advanced cutaneous melanoma receiving MK-3475.
- 2) **Objective:** To evaluate the ORR, DOR, and PFS per irRC assessed by the central independent radiology review in subjects with advanced cutaneous melanoma receiving MK-3475.
- 3) **Objective:** To evaluate the overall survival (OS) in subjects with advanced cutaneous melanoma receiving MK-3475.

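### Duration of response ends at progression only and has no censoring rule for responders, so it would be biased upward if any responder dies without documented progression

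*Combined protocol and SAP*

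**What the plan says.** Section 8.2.3.1 lists the secondary efficacy endpoints in one sentence. Three of them matter here.

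- RECIST 1.1 DOR: "duration of response, defined as time from first RECIST 1.1 response to disease progression in subjects who achieve a PR or better". Death is not mentioned.
- PFS: "the time from allocation to the first documented disease progression according to RECIST 1.1 or death due to any cause, whichever occurs first". Death is an event.
- "duration of response based on irRC": listed by name, with no start, end or censoring of its own.

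Tables 8 and 9 analyse both DOR endpoints in all responders, with the method given as "Summary statistics using Kaplan-Meier method". The only missing-data entry for DOR is "Non-responders are excluded in analysis". That says who is left out, but not how a responder is handled. The entry "Censored at last assessment" stands against PFS and OS, not DOR. The Day 1 censoring rule in Section 8.2.5.1 follows the PFS sentence and concerns subjects with no evaluation or survival data, which a responder cannot be.

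DOR is a stated secondary objective. Section 3.2 reads "To evaluate the duration of response (DOR) and progression-free survival (PFS) per RECIST 1.1 assessed by the central independent radiology review", and its next item covers DOR by irRC. Section 8.2.9 names DOR as one reason for following patients beyond the main analysis. Section 2.1 provides telephone follow-up of every subject for survival, so deaths are collected.

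**The concern.** The plan names death for one endpoint and omits it from the endpoint beside it, and nothing elsewhere supplies the missing rule. If progression is the only event, Kaplan-Meier must treat a responder who dies first as censored. It then credits that subject with the same prospects of continued response as those still at risk. The same subject is a PFS event on the day of death.

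The situation can arise under this protocol. Scans are 12 weeks apart after week 48 and in post-treatment follow-up (Sections 7.1.3.4 and 7.1.5.4.2). Progression for this endpoint is judged by central radiology review, so a responder who dies between scans may have no documented progression.

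At stake are the DOR curve, median and landmark rates in a small responder set. The reader of a single-arm trial will use them to judge how durable the responses are.

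**Working it through.** **Plan's own figure.** The documents give no figure for DOR. The only design figure is the power of the ORR test in Section 8.2.7: 28 evaluable subjects, null 10%, true ORR 35%, success at 7 or more responses, one-sided 2.5%. Exact binomial:

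- P(X >= 7 | 28, 0.35) = 0.908, which reproduces the stated power of about 90%.
- P(X >= 7 | 28, 0.10) = 0.0179, within 0.025. A cut-off of 6 would give 0.0550, so 7 is the smallest valid cut-off.

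DOR enters neither number, so the point leaves both unchanged.

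**Size of the DOR set.** At the design ORR, 28 x 0.35 = 9.8, or about 10 responders; at the minimum success count, 7. One death without progression is therefore 1/10 = 10% or 1/7 = 14% of the set.

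**Effect on the estimate.** Let L be the total hazard of a response ending by progression or death, and s the share of endings that are deaths without documented progression. With constant cause-specific hazards:

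- Median with death as an event: ln 2 / L.
- Median with progression as the only event: ln 2 / (L(1-s)).
- Ratio: 1/(1-s).
- If the true 12-month rate is 50%, the progression-only rate is 0.5^(1-s).

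The documents give neither s nor a median DOR. The shares below and the true median of 12 months are assumptions.

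| s | Ratio 1/(1-s) | Median, 12/(1-s) months | 12-month rate, 0.5^(1-s) |
|---|---|---|---|
| 0 | 1.00 | 12.0 | 50.0% |
| 0.05 | 1.05 | 12.6 | 51.8% |
| 0.10 | 1.11 | 13.3 | 53.6% |
| 0.20 | 1.25 | 15.0 | 57.4% |

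**Small-sample check.** In 10,000 simulated sets per scenario, with follow-up cut at 18 months and the same assumptions, the mean 12-month Kaplan-Meier estimates were as follows for s = 0.05, 0.10 and 0.20.

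| Responders | Death censored | Death as event |
|---|---|---|
| 10 | 51.7%, 53.8%, 57.5% | 49.9%, 50.1%, 50.0% |
| 7 | 52.0%, 53.0%, 57.6% | 50.2%, 49.5%, 50.2% |

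The formula therefore holds at these sizes.

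**Direction.** If the death is censored on its own date, dropping it as an event removes a downward step and adds none, so the curve is nowhere lower. The bias is upward, or zero when no such death occurs.

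**The case against.** The strongest reply is that the effect may be absent, and is small against the noise if present. Under the 12-month model, the expected number of deaths without progression among 10 responders by 12 months of response is 10 x 0.5 x s = 0.25, 0.5 or 1.0 for the three shares. The largest share means 10% of responders dying without progression within a year. Section 4.1.1 reports more than about 80% of all patients alive at one year in the earlier study, non-responders included, so 20% looks like the upper end. Even with all 10 endings observed, a 12-month exponential median has an approximate 95% interval of 12/1.86 = 6.5 to 12 x 1.86 = 22 months, where 1.86 = exp(1.96/sqrt(10)). Scans are also 6 weeks apart from week 12 to week 48, and more frequent if clinically indicated, which narrows the room for an unscanned death.

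All of that stands as a limit on size. It does not supply the missing rule, and a one-directional bias is not excused by a wide interval.

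A reader might also infer four stronger things that the documents do not support:

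- That the reported durations are overstated. This needs at least one responder to die without documented progression, and no section gives a frequency.
- That the plan instructs the analyst to censor deaths. It states no DOR censoring rule; censoring follows only from a progression-only event under Kaplan-Meier.
- That irRC DOR is defined as ending at progression. It has no definition, and the RECIST 1.1 wording is only presumed to carry over.
- That deaths are hidden or trial success is affected. PFS counts every death, OS is reported separately, and the success rule uses ORR alone.

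**Conclusion.** The point holds as a gap in the definition of a secondary endpoint. RECIST 1.1 DOR omits death where PFS includes it, irRC DOR is undefined, and neither has a censoring rule. Following the text as written would not count a responder's death without progression as the end of response, and DOR would then be biased upward.

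The inflation of the median is 1/(1-s), or 5% to 25% for s between 5% and 20%, and zero if there is no such death. This rests on constant cause-specific hazards and on shares that are assumed. The documents allow the direction to be stated but not the size. DOR is descriptive, so the ORR test, its alpha and its power do not move. The definition should be corrected, but the trial's main conclusion does not depend on it.

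**What to change.** In Section 8.2.3.1, define DOR for RECIST 1.1 and for irRC separately as the time from first response under that criterion to the earlier of documented progression under that criterion and death from any cause.

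In the DOR rows of Tables 8 and 9, add two censoring rules:

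- A responder with neither progression nor death is censored at the last tumour assessment.
- A responder who starts a new anti-cancer therapy, including marketed MK-3475, without prior progression is censored at the last tumour assessment before that therapy.

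The second rule is needed because disease-status follow-up stops at such therapy (Section 1.0; Section 6.1, note 2) while survival follow-up continues. Adding death alone would count a subject who switched as responding until a death that may come much later, which would lengthen DOR again.

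The cost is a revised definition and revised table entries. No new data are needed, because deaths and subsequent therapy are already recorded. Reported DOR may be slightly shorter. The current amendment deals with the period around marketing approval, and Section 8.2.9 places the main analysis before filing, so the change may come after open-label data have been seen. If so, it must be reported as such; showing DOR under both definitions would let the reader see whether it mattered.
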